5.2.1 Reasons for Withdrawal/Discontinuation

Patients may withdraw from treatment at any time and for any reason, without prejudice to their future medical care. Patients may also be withdrawn by the Investigator or others at the study site.

A patient may be withdrawn from treatment for any of the following reasons:

- Disease progression.
- AE.
- Withdrawal of consent.
- Major protocol deviation.
- Required treatment delay >21 days (except in case of potential patient benefit, which must be approved by the Sponsor).
- Non-compliance, including lost to follow-up.
- Pregnancy.
- Other (e.g., development of contraindications).

- The Investigator determines it is in the best interest of the patient to discontinue the patient's participation in the study.
- Discontinuation of the study by the Sponsor.
- Death.

Note: Patient enrollment will be halted, pending a safety analysis and review with the appropriate regulatory authority(ies), if any patient in Part 1 or Part 2 experiences a CTCAE Grade 5 AE, or 2 non-hematologic CTCAE Grade 4 AEs, which are not attributable to the underlying disease, and for which relationship to ADCT-301 cannot be ruled out, within 30 days of their last dose of ADCT-301.

Note: Patients who experience a DLT during Cycle 1 are to be permanently discontinued from the study.

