- Any patient who experiences a recurrent CTCAE Grade 3 or 4 toxicity, excluding hematological toxicity.
- Any patient who requires a dosing delay >21 consecutive days from the planned Day 1 dosing at any time during treatment (except in case of potential patient benefit, which must be approved by the Sponsor).

Neurological toxicities: dose delay/permanent discontinuation

Patients experiencing any new neurological toxicities \geq Grade 1, not explained by previous medical history, that could be linked to or may be an early indicator of polyradiculopathy/GBS, such as ascending (bilateral) sensory loss or motor weakness, need to be immediately evaluated by a neurologist and dosing of ADCT-301 needs to be delayed until polyradiculopathy/GBS is ruled out. Should further clinical, radiologic, or laboratory evidence support the diagnosis of polyradiculopathy/GBS with the level 1 of diagnostic certainty ([Appendix 13.3](#)), treatment with ADCT-301 must be stopped and patient must be permanently discontinued.

Patients with Grade \geq 3 neurologic toxicities, defined as peripheral sensory and peripherally motor neuropathies, must be permanently discontinued.

Other new neurological findings not explained by previous medical history increase of \geq 1 grade over baseline will result in dose delay; dosing may be resumed after resolution to baseline, at the investigator's discretion. The patient must be carefully monitored at least weekly until such resolution (can be done by telephone unless symptoms worsen).

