6.5 Study Stopping Rules

The study will be stopped if any of the following circumstances occur:

- Two additional patients (from date of December 14, 2017) develop polyradiculopathy/GBS (Level 1 of diagnostic certainty; [Appendix 13.3](#)). Continuation of patients who have shown clinical benefit will be discussed with the relevant regulatory authority(ies) if this stopping rule is applied.
- \geq 30% of patients experience a specific Grade 4 or higher non-hematologic treatment-emergent AE.

Furthermore, patient enrollment will be halted, pending a safety analysis and review with the relevant regulatory authority(ies):

- if any patient in Part 1 or Part 2 experiences a CTCAE Grade 5 AE, or 2 non-hematologic CTCAE Grade 4 AEs, which is not attributable to the underlying disease, and for which relationship to ADCT-301 cannot be ruled out, within 30 days of their last dose of ADCT-301.
- in the event of another single case of GBS. Patients currently on trial having clinical benefit or not yet having reached first bone marrow assessment can continue on study once informed and they consent to continue treatment.

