6.10.3 Diagnostic, Work-up and Management of Polyradiculopathy / Guillain-Barré Syndrome

It is recommended starting management of polyradiculopathy/GBS with either IVIg 0.4 g/kg/day for 5 days or plasma exchange (PLEX) once diagnosis of polyradiculopathy/GBS has been considered by a neurologist; this would be at CTCAE Grade 2 symptoms for neuropathy or Score 1 as per GBS disability scale ([Appendix 13.4](#)).

Diagnostic workup should include:

- Neurology consultation
- MRI spine with and without contrast to rule out compressive lesion and evaluate for nerve root enhancement or thickening
- Electrodiagnostic studies (nerve conduction studies)
- Pulmonary function tests
- Lumbar puncture: CSF typically has albuminocytologic dissociation with protein elevation disproportionate to WBC—although note that CSF WBC are often elevated in GBS associated with immune checkpoint inhibitors
- Serum antibody testing for GBS (ganglioside antibodies) when possible

Management includes:

- IVIg or PLEX as above
- If IVIg and/or PLEX do not result in improvement, consider using steroids (Gu 2017)¹⁵
- Admission to inpatient unit with capability for rapid transfer to ICU-level monitoring
- Frequent focused neurological examination (at least twice daily)
- Frequent pulmonary function monitoring
- Monitoring for autonomic dysfunction
- Non-opioid management of neuropathic pain
- Treatment of constipation/ileus
- Anticoagulation
- Physical therapy

7 Study Assessments and Procedures

Patients will undergo the procedures at the time points specified in schedule of events ([Appendix 13.1](#)).

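### The single-case enrolment halt names only GBS and the two-patient stop counts only a GBS case definition, so a drug-related non-GBS polyradiculopathy forces no enrolment pause of its own

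*Protocol*

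**What the plan says.** Protocol 6.5 sets two neurological triggers at trial level.

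- **Enrolment halt.** Enrolment is paused, pending a safety analysis and regulatory review, "in the event of another single case of GBS". The synopsis has the same trigger. It carries no condition on causality, severity, diagnostic certainty or timing.
- **Study stop.** The study stops if "Two additional patients (from date of December 14, 2017) develop polyradiculopathy/GBS (Level 1 of diagnostic certainty", with a pointer to Appendix 13.3. That appendix gives Level 1 criteria for Guillain-Barré syndrome only. All of them must be met, including GBS-type electrophysiology, cytoalbuminologic dissociation and no alternative diagnosis.

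The halt note in 5.2.1 begins "Patient enrollment will be halted, pending a safety analysis and review with the appropriate regulatory authority(ies), if any patient" and goes on to the general severity trigger only. It mentions neither GBS nor polyradiculopathy.

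At patient level the wider term is used. Under 6.4, when a new neurological toxicity could point to either condition, "dosing of ADCT-301 needs to be delayed until polyradiculopathy/GBS is ruled out". Section 6.10.3 gives one work-up and management plan for both.

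**The concern.** The protocol does not treat the two terms as interchangeable. Exclusion criterion 8 presents GBS as one form of polyradiculopathy. The summary of changes gives reports of both GBS and polyradiculopathy in treated patients as the basis for Amendment 5, though without counts and without saying how clearly they were told apart.

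A single-case halt exists so that a pause before further dosing does not depend on anyone's discretion. As worded, whether the pause happens depends on which of two labels a neurologist gives to the case. The stop rule appears to cover both, but its Level 1 condition can be met only by GBS, so naming polyradiculopathy there has no effect for a non-GBS case.

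**Working it through.** The plan states no operating characteristic for these rules and no event rate, so there is no figure to reproduce and no probability is offered. The check applies each rule to one drug-related polyradiculopathy diagnosed as non-GBS.

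| Rule | What fires it | Effect of the case |
|---|---|---|
| Single-case halt (6.5, synopsis) | One further GBS case | 0 of 1 |
| Two-patient stop (6.5, App. 13.3) | Two Level 1 cases | 0 of 2, as Level 1 exists only for GBS |
| Severity halt (6.5, synopsis, 5.2.1) | A Grade 5 AE, or two non-hematologic Grade 4 AEs, possibly drug-related, no later than 30 days after last dose | None at Grades 1 to 3 or for a single Grade 4 AE |
| 30% stop (6.5) | At least 30% of patients with one particular non-hematologic event of Grade 4 or above | One case does not reach it |
| DLT rule (7.3.1.1, 4.1.1) | Peripheral neuropathy of Grade 2 or above in Cycle 1 | Acts through 3+3 only |

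Three rows need comment.

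- **Severity halt.** It applies to an event "which is not attributable to the underlying disease, and for which relationship to ADCT-301 cannot be ruled out". A fatal related case inside 30 days would therefore halt enrolment, through the severity rule and not because it is a polyradiculopathy.
- **30% stop.** Section 6.5 does not state the denominator. If it were only the nine patients allowed after Amendment 5, the threshold would be 0.30 × 9 = 2.7, that is 3 patients.
- **DLT rule.** One DLT among three patients leads to up to three more at the same dose. A further DLT among those closes that dose and sets the preceding one as the MTD. Neither outcome halts enrolment to the trial.

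**Exposure.** Section 4.1.1 allows 9 more escalation patients from the date of Amendment 5.

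- Case in one of the nine: at most 9 − 1 = 8 further planned patients without a mandatory pause.
- Case in a patient enrolled before the amendment: at most 9 − 0 = 9.
- The cap lifts if two additional patients reach PR, CR or CRi, so neither number is a hard ceiling.

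**What does operate for such a case.**

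- Dosing is held (6.4). Withdrawal then follows for "Any patient who requires a dosing delay >21 consecutive days from the planned Day 1 dosing", unless the sponsor approves an exception. Grade 3 or higher peripheral sensory or motor neuropathy means permanent discontinuation.
- Management in 6.10.3 includes "Admission to inpatient unit with capability for rapid transfer to ICU-level monitoring". Admission makes the event an SAE (7.3.2.1), due to the CRO within 24 hours (7.3.2.3). If it is at least possibly related it is a SUSAR (7.3.2.5), and 10.6 sends it to the FDA, EU authorities and the ethics committee.
- The DESC reviews safety monthly or more often and decides dose levels (7.3.1.2).

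With a separate non-GBS trigger, the same case would count 1 of 1 toward a halt. It would still count 0 of 2 toward the stop.

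**The case against.** **The halt may be shorthand.** Sections 6.4, 6.5 and 6.10.3 handle polyradiculopathy/GBS as one composite, and the stop rule applies Level 1 to that composite. The halt may have been meant the same way. Exclusion criterion 8 and the basis for Amendment 5 point the other way. The intent is unclear, and an unclear trigger is itself a reason to settle the wording.

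**The gap is narrow.** This stands. Only a polyradiculopathy affirmatively called non-GBS is left out.

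**A carve-out could do harm.** This stands too. Today's GBS trigger is unconditional. An exception for other identified causes, attached to the whole bullet, could exempt a GBS case put down to one of the infections listed in 7.3.4.5, which now halts enrolment. Any exclusion must attach to the new trigger alone.

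**The new term is undefined.** This stands in part. The protocol has no case definition for non-GBS polyradiculopathy. The trigger has to rest on a neurologist's diagnosis after the 6.10.3 work-up, which leaves some judgment.

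A reader might also infer more than the text supports:

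- *That GBS short of Level 1 escapes the halt.* It does not; Level 1 limits the stop, not the halt.
- *That regulators would not hear of the case, or that the patient would go on being dosed.* The reporting and dose-hold rules say otherwise.
- *That the share of follow-up outside the 21-day DLT window measures the gap.* It does not, because a Cycle 1 DLT does not halt enrolment either.
- *That the safety analysis would miss such cases.* SAP 4.8.2.1 lists neurologic events by three standardized queries, without a Level 1 filter.

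**Conclusion.** The concern holds in a limited form. A related non-GBS polyradiculopathy of Grade 1 to 3, or one that amounts to a single Grade 4 AE, triggers no mandatory enrolment pause under the protocol as written. Enrolment continues unless the DESC, the sponsor or a regulator chooses to act. The size is 0 of 1 toward the halt and 0 of 2 toward the stop, with at most 8 or 9 further planned escalation patients exposed to that discretion, subject to the cap not lifting.

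This rests on reading GBS in the halt literally and on the neurologist separating the two diagnoses. The expedited reporting route assumes that the patient is admitted as 6.10.3 advises, or that the event is otherwise judged serious. SAP 3.3 says the trial ended before dose escalation was complete, so the point concerns the protocol's wording for Part 1 and not the reported analysis. It is a low-cost safety improvement to a trigger, not a failure of safety oversight.

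**What to change.** Leave the GBS trigger exactly as it is and add a second, separate one after it in 6.5 and the synopsis:

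> or in the event of a single case of neurologist-diagnosed non-GBS polyradiculopathy (after the 6.10.3 work-up) not clearly due to underlying leukemia or a compressive lesion.

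Carry both triggers into the halt note in 5.2.1. Keep Level 1 as the threshold for the two-patient stop; the safety review that follows a halt can decide what a non-GBS case means for continuing.

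The exclusion follows the logic of the DLT definition, which leaves out events clearly due to disease or extraneous causes, but it is confined to two causes and does not touch GBS. The tests needed are already listed in 6.10.3, including neurology consultation, nerve conduction studies, lumbar puncture and "MRI spine with and without contrast to rule out compressive lesion".

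The text changes in three places. The real cost is a protocol amendment, which under 11.2.1 goes through the same review and approval as the original protocol, and an occasional pause for a case later found unrelated to the drug.

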6.6 Identity of Investigational Product

ADC Therapeutics will provide and distribute adequate supplies of ADCT-301 to the study sites. The following drug supplies will be used in the study:

Product	Supplied As
ADCT-301	10-mL glass vial at a deliverable volume of 5.4 mL at 6 mg/mL (equivalent to 30 mg ADCT-301)

6.6.1 ADCT-301 Drug Product

ADCT-301 is a sterile formulation containing PBD-conjugated HuMax[®]-TAC (DAR \geq 1), HuMax[®]-TAC (DAR = 0), and SG3249. It is provided pre-formulated in 10-mL glass vials containing approximately 30 mg ADCT-301 per vial (deliverable volume 5.4 mL at 6 mg/mL).

6.7 Management of Clinical Supplies

6.7.1 Study Drug Packaging and Storage

ADCT-301 will be supplied in a labeled 10-mL stoppered glass vial and shipped by Fisher Clinical Services to the investigational site. Once the package arrives, the receiving site pharmacy will complete the enclosed procedures to acknowledge receipt.

All study drugs must be stored in a secure area (e.g., a locked cabinet). ADCT-301 should be protected from light and stored frozen (-65°C or below). ADCT-301 should be thawed under ambient conditions.

6.7.2 Study Drug Preparation and Administration

After the vials have been completely thawed, they should be gently mixed by swirling to ensure homogeneity and visually inspected before use. The appropriate quantity of ADCT-301 will be removed from the vial with a syringe and diluted into a 50 mL IV bag containing 5% dextrose in water (D5W). The amount of the product to be diluted will depend on the dose level and the body mass of the patient. Once the ADCT-301 has been transferred, the bag should be mixed to ensure homogeneity of the dosing solution. The contents of the IV bag will then be administered to the patient with a dosing pump per institutional guidelines for intravenous fluid (IVF) administration.

Additional instructions regarding study drug handling, storage, and preparation are included in the Pharmacy Manual.

6.7.3 Study Drug Accountability

The Investigator will maintain accurate records of receipt of all study drugs, including dates of receipt. In addition, accurate records will be kept regarding when and how much study drug is dispensed and used by each patient in the study. Reasons for departure from the expected dispensing regimen must also be recorded. All study drugs will be reconciled and retained or destroyed according to applicable regulations.

6.8 Overdose Management

An overdose is any dose of study treatment given to a patient that exceeds the dose described in the protocol. Any overdose, with or without associated AEs, must be promptly reported to the Sponsor. There are no data available to determine what effects and whether effects of an overdose can be reversed. Symptomatic treatment and standard supportive care measures for the management of this toxicity should be applied.

6.9 Treatment Compliance

Administration of the study treatments will be performed by the Investigator or a qualified designee; therefore, compliance will be verified by the study drug administration information.

6.10 Concomitant Treatment

All medications used within 14 days prior to the Day 1 visit and during the treatment period are to be recorded in the eCRF. Concomitant medication information will be collected for 30 days following the patient's last dose of ADCT-301. This will include all prescription drugs, herbal products, vitamins, minerals, and over-the-counter medications. Any changes in concomitant medications will also be recorded in the patient's eCRF.

6.10.1 Prohibited During Study

- Other anti-cancer therapy, with the exception of hormonal therapy for maintenance treatment of breast and prostate cancer.
- Hydroxyurea is not permitted after Cycle 1 unless approved by the Sponsor.
- Other investigational agents.
- Chronic treatment with corticosteroids (prednisone ≥ 12.5 mg/day or dexamethasone ≥ 2 mg/day, excluding inhaled steroids).
- Live vaccines.

6.10.2 Permitted During Study

After confirmation and documentation of eligibility, supportive care treatments (transfusions, etc.) can be prescribed as medically appropriate. Hematopoietic growth factors are permitted as per the American Society of Clinical Oncology guidelines;³¹ however, prophylactic use of growth factors is not allowed during the first treatment cycle.

Patients with a WBC value $>15,000$ cells/ μL at the Screening Visit may receive hydroxyurea prior to and during the first cycle of treatment and/or leukopheresis to lower the WBC value to $<15,000$ cells/ μL prior to study drug administration on Day 1, Cycle 1 ([Section 5.1.1](#)).

If CTCAE Grade 2 or higher infusion-related hypersensitivity reactions are observed in 1 patient at any time during Part 1 of the study, all subsequent patients must receive prophylactic treatment ([Section 6.2](#)).

Concomitant steroid use is permitted as follows:

- Replacement doses of steroids for patients with adrenal insufficiency.
- Intranasal, inhaled, topical steroids, or local steroid injections (e.g., intra-articular injection)
- Intrathecal medication for CNS prophylaxis (not for active disease) per institutional standard of care practices.
- Prophylactic treatment with dexamethasone as follows may be instituted by the DESC based on emerging safety and PK profile:
 - Dexamethasone 4 mg oral BID the day before investigational product (IP) administration, the day of IP administration, and the day after IP administration (Week 1/Day 1 of each cycle only, regardless of treatment schedule).
 - A 2-day course of dexamethasone 4 mg PO BID will be given (Week 1/Days 1 and 2 of each cycle). If possible, the first dose should be given at least 2 hours prior to IP administration.

Any concomitant medication deemed necessary for the welfare of the patient during the study may be given at the discretion of the Investigator.

6.10.3 Diagnostic, Work-up and Management of Polyradiculopathy / Guillain-Barré Syndrome

It is recommended starting management of polyradiculopathy/GBS with either IVIg 0.4 g/kg/day for 5 days or plasma exchange (PLEX) once diagnosis of polyradiculopathy/GBS has been considered by a neurologist; this would be at CTCAE Grade 2 symptoms for neuropathy or Score 1 as per GBS disability scale ([Appendix 13.4](#)).

Diagnostic workup should include:

- Neurology consultation
- MRI spine with and without contrast to rule out compressive lesion and evaluate for nerve root enhancement or thickening
- Electrodiagnostic studies (nerve conduction studies)
- Pulmonary function tests
- Lumbar puncture: CSF typically has albuminocytologic dissociation with protein elevation disproportionate to WBC—although note that CSF WBC are often elevated in GBS associated with immune checkpoint inhibitors
- Serum antibody testing for GBS (ganglioside antibodies) when possible

Management includes:

- IVIg or PLEX as above
- If IVIg and/or PLEX do not result in improvement, consider using steroids (Gu 2017)¹⁵
- Admission to inpatient unit with capability for rapid transfer to ICU-level monitoring
- Frequent focused neurological examination (at least twice daily)
- Frequent pulmonary function monitoring
- Monitoring for autonomic dysfunction
- Non-opioid management of neuropathic pain
- Treatment of constipation/ileus
- Anticoagulation
- Physical therapy

7 Study Assessments and Procedures

Patients will undergo the procedures at the time points specified in schedule of events ([Appendix 13.1](#)).

7.1 Efficacy Assessments

Assessment of response to treatment with ADCT-301 will be based on bone marrow samples (aspirate or biopsy if aspirate unattainable). Bone marrow samples will be obtained as described in [Section 5.1.7.1](#) and [Table 1](#) and [Table 3](#) for the Q3W and QW dosing schedules, respectively.

The activity of ADCT-301 will be evaluated based on the Investigator's evaluation of the patient's response to ADCT-301 as CR, CRi, PR, PD or NR. ^{8,11}

- Complete response is defined as achieving each of the following:
 - Bone marrow differential showing $\leq 5\%$ blast cells and absence of blast cells with Auer rods.
 - Absolute neutrophil count $\geq 1.0 \times 10^9/L$ and platelet count $\geq 100 \times 10^9/L$.
 - Absence of extramedullary disease.
 - Patient is independent of red blood cell (RBC) transfusions.
- Complete response with incomplete blood count recovery is defined as achieving all CR criteria except that values for ANC may be $< 1.0 \times 10^9/L$ and/or values for platelets may be $< 100 \times 10^9/L$.
- Partial response is defined as achieving each of the following:
 - Absolute neutrophil count $\geq 1.0 \times 10^9/L$ and platelet count $\geq 100 \times 10^9/L$.
 - Bone marrow differential showing a $\geq 50\%$ decrease from baseline in the percentage of bone marrow blast cells to a level $> 5\%$ and $\leq 25\%$,
or
bone marrow differential showing $< 5\%$ blast cells and presence of Auer rods.
- No response is defined as not achieving CR, CRi, or PR.
- Progressive disease is defined as:
 - For patients with CR or CRi, the first date of reappearance of blast cells in bone marrow and/or peripheral blood to a level $\geq 5\%$, or development of extramedullary disease.
 - For patients with PR, the first date of an increase in blast cells in bone marrow and/or peripheral blood such that the patient does not continue to meet the criteria for PR.

As defined in [Section 8.6.2](#), DOR and ORR will be defined among responders (CR, CRi, PR); OS and PFS will also be determined.

[REDACTED]

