No more than 9 additional patients (e.g., 3 cohorts of 3 patients) will be enrolled in the remaining dose escalation portion of this study (max. dose level 50 µg/kg/week) from the date of protocol amendment number 5, unless 2 additional patients attain a PR, CR, or CRi, in which case additional patients will be treated at a dose patients have cleared the DLT period, to determine if there is sufficient evidence of clinical activity to continue the study.

No more than 10 patients in total can be treated at any dose level unless ≥ 3 of the 10 patients have achieved a PR or better.

Every 3-Week Administration

Patients will be given ADCT-301 on Day 1 of each 3-week treatment cycle.

When the dose is escalated, the dose may increase by 100% if no DLTs are observed at the current level (e.g., at 6 µg/kg, the dose increase is 6 µg/kg). Once a DLT is observed at a given dose level, the next dose may only increase by 50% (e.g., at 6 µg/kg, the dose increase is 3 µg/kg). The dose may never increase by more than 100%, or more than an absolute value of 20 µg/kg at dose levels below 100 µg/kg and 50 µg/kg for dose levels between 100 and 150 µg/kg, whichever is less.

Weekly Administration

Patients will be given ADCT-301 (QW) on Days 1, 8, and 15 of each 3-week treatment cycle.

The first dose level for the QW dosing will be based on the safety and tolerability of patients who have been treated on the Q3W schedule. The first 3 patients will be given a cumulative dose each cycle that is comparable to (but not higher than) the highest dose tested at the Q3W dose schedule at which 3 patients completed the DLT observation period without a DLT. For example, if the highest Q3W dose tested at which 3 patients did not experience a DLT was cohort 92 µg/kg, the first cohort to receive (QW) dosing will receive 30 µg/kg each week for 3 weeks.

When the dose is escalated, the dose may increase by 50% if no DLTs are observed at the current level. Once a DLT is observed at a given dose level, the next dose may only increase by 25%. The dose may never increase by more than 50%, or more than an absolute value of 20 µg/kg/week, whichever is less.

A patient will maintain the same treatment schedule throughout the duration of the trial.

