8.6.2.1 Duration of Response

Duration of response will be defined among responders (CR, CRi, or PR) as the time from the earliest date of first response until the first date of either disease progression or death due to any cause. The date of disease progression is defined for patients with CR or CRi as the first date of reappearance of blast cells in bone marrow and/or peripheral blood to a level $\geq 5\%$, or development of extramedullary disease. In patients with PR, it is defined as the first date of an increase in blast cells in bone marrow and/or peripheral blood such that the patient does not continue to meet the criteria for PR (Section 7.1). For patients whose disease has not progressed or who have not died at the time of the analysis, censoring will be performed using the date of the last disease assessment. In addition, patients with disease progression or who have died after an extended loss to follow-up by the investigative site will be censored at the date of the last disease assessment prior to the extended loss to follow-up. Further details on censoring rules will be outlined in the SAP.

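### Response and progression definitions cover different disease compartments: new extramedullary disease does not end a PR, and no response category limits circulating blasts

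*Protocol*

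**What the plan says.** Protocol 7.1, repeated in the synopsis, sets out the categories. The basis is stated first: "Assessment of response to treatment with ADCT-301 will be based on bone marrow samples". The list for CR opens with "Complete response is defined as achieving each of the following" and has four parts:

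- a marrow differential of at most 5% "blast cells and absence of blast cells with Auer rods"
- ANC and platelet thresholds
- "Absence of extramedullary disease"
- independence from red-cell transfusion

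For the next category, "Complete response with incomplete blood count recovery is defined as achieving all CR criteria except that values for ANC may be" below the CR threshold, and likewise platelets. PR needs the CR count thresholds plus a marrow reduction, or low marrow blasts with Auer rods. It mentions neither blood blasts nor extramedullary disease.

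Progression after CR or CRi is blasts of 5% or more in marrow and/or blood, or new extramedullary disease. The rule after PR is "For patients with PR, the first date of an increase in blast cells in bone marrow and/or peripheral blood such that the patient" falls outside the PR criteria. Section 8.6.2.1 repeats this for DOR: "In patients with PR, it is defined as the first date of an increase in blast cells in bone marrow and/or peripheral blood". Section 8.6.2.4 does the same for PFS.

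Section 4.1.1 ties Part 1 enrolment to response:

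- One PR or better is needed before patients can be added at a lower level.
- Two further responses lift the cap of 9 additional patients set at amendment 5.
- "No more than 10 patients in total can be treated at any dose level unless" at least 3 of those 10 reach PR or better.

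Section 7.3.4.1 puts peripheral blasts in the hematology analysis for Part 2 only. SAP 3.3 says that the trial ended during Part 1 and that only Part 1 is analysed. SAP 4.9 lists efficacy data without summaries.

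**The concern.** The protocol treats blood blasts and extramedullary disease as leukemia activity in one rule and leaves them out of neighbouring rules. Three gaps follow.

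(a) New extramedullary disease ends a CR or CRi but not a PR.

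(b) A patient with circulating blasts can enter CR, CRi or PR, although blood blasts at 5% are progression once CR or CRi has been called.

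(c) The blood part of progression after PR refers back to criteria that contain no blood limit, so it cannot act alone.

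At stake are the accuracy of the CR/CRi/PR/PD calls that will be listed and, through (b), enrolment decisions that turn on one, two or three responses.

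**Working it through.** The plan states no figure that depends on these definitions, so there is nothing to reproduce. The check sets the rules side by side and applies them as written.

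**Inputs (Protocol 7.1; counts in 10^9/L)**

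| Rule | Marrow blasts | Blood blasts | Extramedullary disease | Counts |
|---|---|---|---|---|
| CR | ≤5%, no Auer rods | no criterion | must be absent | ANC ≥1.0, platelets ≥100, no red-cell transfusion need |
| CRi | as CR | no criterion | must be absent | ANC and/or platelets may be lower |
| PR | ≥50% fall to >5% and ≤25%, or <5% with Auer rods | no criterion | no criterion | ANC ≥1.0, platelets ≥100 |
| PD after CR/CRi | ≥5% | ≥5% | new disease | none |
| PD after PR | rise that loses PR | rise that loses PR | not mentioned | only through the PR criteria |

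The CR/CRi progression rule names blood blasts and extramedullary disease as separate items. Absence of extramedullary disease therefore cannot be read as covering circulating blasts.

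**Test patients**

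1. Marrow 3%, no Auer rods, ANC 1.2, platelets 120, no extramedullary disease, transfusion-independent. Blood blasts of 4%, 10% or 20%: CR each time. At 10% and 20% the patient is also above the 5% progression level. Because that rule speaks of reappearance, the patient is either CR and PD on one date, or not PD because the blasts never went away. At 4% no rule applies to the blood blasts.
2. The same marrow with ANC 0.4, platelets 40 and 20% blood blasts: CRi.
3. Marrow 15% from a baseline of 40%, a fall of (40 − 15)/40 = 62.5%, with ANC 1.2 and platelets 120. Blood blasts of 0%, 20% or 30%: PR each time.
4. Patient 3 with new extramedullary disease and unchanged marrow, blood and counts: still PR, progression not triggered. This is gap (a).
5. Patient 3 with blood blasts rising from 0% to 30%, marrow and counts unchanged: still PR, progression not triggered. This is gap (c).
6. Patient 5 with platelets also falling below 100: PR is lost and progression is triggered. The blood limb works only together with another failure.

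**Sensitivity of the enrolment rules to over-called responses (illustration)**

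The documents give no response rate, so the apparent rate p is an assumption, with independent patients. For the second rule, the two responses are assumed to come from the 9 additional patients.

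- P(≥3 of 10) = 1 − Σ(k = 0 to 2) C(10,k) p^k (1−p)^(10−k). At p = 0.10: 1 − (0.3487 + 0.3874 + 0.1937) = 0.070.
- P(≥2 of 9) = 1 − (1−p)^9 − 9p(1−p)^8. At p = 0.10: 1 − 0.3874 − 0.3874 = 0.225.

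| Apparent response rate | P(≥3 of 10) | P(≥2 of 9) |
|---|---|---|
| 5% | 0.012 | 0.071 |
| 10% | 0.070 | 0.225 |
| 15% | 0.180 | 0.401 |
| 20% | 0.322 | 0.564 |
| 25% | 0.474 | 0.700 |

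Over-called responses would loosen both rules. The table does not say how often over-calling happens.

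**The case against.** The best defence is that a marrow-based response is a stated choice, judged by the Investigator with two published criteria papers cited, and that efficacy data are only listed. The first part does not close the gaps. The protocol writes out its own definitions, and an Investigator who applied stricter ones would depart from them, so identical patients could be classified differently. What the cited papers require was not used here. The second part stands and limits the effect.

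Several stronger readings are tempting but unsupported:

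- A reader might infer that false responders inflate ORR and that DOR and PFS miss progression. Under SAP 4.9 none of these is summarised.
- A reader might infer that all three gaps distort enrolment. The Section 4.1.1 rules count responses attained, so progression missed after PR, gaps (a) and (c), does not change them. The lower-level rule is also permissive: the steering committee may add patients but need not.
- A reader might infer that the blood limb after PR can never act. Test patient 6 shows that it can when a count also falls.
- A reader might treat one misclassified patient as one third, one half or all of the responses required. That restates the thresholds 3, 2 and 1 and does not estimate misclassification.
- A reader might explain low marrow blasts beside higher blood blasts by a hemodilute aspirate. Mixing in blood with more blasts raises the reading, so dilution does not hide disease in that case.

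**Conclusion.** The point holds as an inconsistency within the protocol. Applied as written, the rules keep a PR patient with new extramedullary disease in response, admit patients with circulating blasts to CR, CRi and PR, and leave the blood limb after PR unable to act alone. The first gap is the clearest, because the missing item already stands in the neighbouring rule. The effect is confined to the listed response and progression calls and, for the entry gap only, to Part 1 enrolment rules that turn on 1 response, 2 responses or 3 of 10. The number of patients affected cannot be derived from the documents. The conclusion assumes that sites apply the definitions as printed. It is worth correcting, but it does not undermine the safety objectives or any planned summary analysis.

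**What to change.** 1. Add new extramedullary disease as a progression event after PR, in the terms already used after CR/CRi, in 7.1, the synopsis, 8.6.2.1 and 8.6.2.4.
2. Set one consistent circulating-blast limit for entry to CR, CRi and PR and for progression from each. Word it so that nobody is responder and PD on the same date, and so that low marrow blasts with some blood blasts has a defined category. Partial changes would fail:
   - Requiring zero blood blasts for CR and CRi alone turns a patient with 3% marrow blasts, no Auer rods and 1% blood blasts into NR, while a fall in marrow blasts from 40% to 20% with adequate counts remains PR.
   - Making 5% blood blasts progression after PR without an entry limit lets a patient with 6% be PR and PD together.
3. Amend 7.3.4.1 so that peripheral blasts are recorded in Part 1 as well as Part 2, and say how the limit applies when WBC is below 400 × 10^6/L and no differential is required.

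The cost is the rewording, a small Part 1 data-collection change that uses the CBC differential already taken, and possibly a slightly lower response count. Since the trial stopped in Part 1, rewording cannot alter enrolment decisions already made. It governs how the listed calls are read and any reuse of these definitions.
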